#### 13.2 Randomization/Stratification

Not applicable.

# 13.3 Accrual and Feasibility

Sample size: Consent/enrollment = 180; Intervention = 96; Analytic sample = 64 after drop-outs. The expected accrual rate is 10 participants per month across five sites, and the planned recruitment duration is 18 months. We anticipate that all evaluable participants will have completed all study procedures within 36 months.

Initial accrual estimates were calculated based on; 1) the number of kidney transplant candidates aged 18-49 who come forward for kidney transplant who eventually get transplanted; and 2) the number of kidney transplants performed in this age sub-set at the five participating transplant centers in 2017.

After accounting for experiences in recruitment of participants during the years the protocol has been open, as well as the additional accrual and retention challenges encountered due to the COVID-19 pandemic, it was projected that the expected accrual for the study will be in the range of n=24 to 28 participants who will receive one or more vaccine doses pre-transplant and complete the necessary post-transplant follow-up period for the primary endpoint analysis.

# 13.4 Primary Objective, Endpoint(s), Analysis Plan

The primary objective is to estimate HPV vaccine-type-specific seroconversion rates at 12-months post-transplantation among kidney transplant recipients who receive  $\geq 1$  doses of the Gardasil® 9 HPV vaccine prior to transplantation,

An estimate of the seroconversion rate will be provided along with exact Clopper-Pearson 95% confidence intervals (CIs).

Originally (until version 3.10), the study was designed with the expectation of at least n=64 evaluable participants for the primary analysis, and the analytic plan was focused on comparisons with prespecified benchmarks (e.g., 0.75 and 0.90) of the expected seroconversion rate estimate.

In version 3.11, responding to the lower accrual expectations of between n=24 to n=28 evaluable participants in the study, the study's focus was revised to only focus on description of the estimation of the seroconversion rate and the upper limit of its one sided 95% confidence interval, as opposed to any pre-specified comparisons.

Even without pre-specified comparison benchmarks, the revised analysis plan will permit cross-study comparisons with other relevant HPV vaccination studies (e.g., those conducted among individuals undergoing solid organ transplants or other immunosuppressed individuals). The study will generate key preliminary data for testing clinically relevant hypotheses in future larger studies to evaluate the full extent of protection afforded by HPV vaccination administered prior to transplant.

With the study expecting to yield between n=24 to n=28 evaluable participants, Table 3 (below) provides expected upper limits of the one sided 95% CI for the estimates of the seroconversion rates ranging between 0.65 to 0.90.

Table 3. Expected upper limits of one sided 95% CI for seroconversion rates				
Expected accrual n=24 evaluable	Expected accrual n=28 evaluable			
participants	participants			

	One-sided 95%CI		One-sided 95%CI
Estimate P	Upper Limit	Estimate P	Upper Limit
0.65	0.8088	0.65	0.7977
0.70	0.8480	0.70	0.8380
0.75	0.8851	0.75	0.8763
0.80	0.9197	0.80	0.9123
0.90	0.9776	0.90	0.9739

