Given the strong biological rationale, a recently convened International Agency for Research on Cancer/National Cancer Institute workshop has recommended seroconversion, and specifically immunological non-inferiority, as sufficient for a presumption of efficacy for the HPV vaccine in immunobridging studies focused on the expansion of vaccine indications [14]. Thus, the endpoint for this trial is seroconversion, and we will define efficacy as greater than or equal to 90% of the study population achieving seroconversion. The definition for positivity, or seroconversion, will be based on results of the HPV-9 cLIA (Merck) or, alternatively, a validated 9-valent HPV multiplex assay developed at the NCI Frederick National Laboratory for Cancer Research (FNLCR), which measures HPV type-specific antibodies to neutralizing epitopes on VLPs from a patient's serum sample. Seropositivity is not part of the eligibility criteria for enrollment.

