Sexual Behavior, Detectable HPV Infection, and Vaccine-Induced Seroconversion. The possibility that reactivation of latent HPV infection may occur with immunosuppression is supported by descriptive clinical studies, but the potential of vaccination to suppress this reactivation is untested. Only a few studies have examined the prevalence of oral/anal/genital HPV in renal transplant recipients, generally following transplant [17]. The first longitudinal study of cervical-vaginal HPV prevalence before and after renal transplant found an increase from 19% pre-transplant to 31% post-transplant [18]. This increase occurred in the absence of reported changes in sexual behavior, suggesting re-activation of latent viral infection. Although the clinical impact of these findings are presently uncertain, an increased prevalence of cervical-vaginal HPV in the absence of person-to-person transmission has implications for patient management [19]. This will be the first study among renal transplant recipients to show whether there is a difference in Gardasil® 9-associated seroconversion between individuals with detectable versus undetectable HPV infections (cervical-vaginal and oral) that cannot be explained by sexual behavior.

**Hypothesis:** The Gardasil® 9 nonavalent vaccine given before the solid organ transplant procedure will induce and maintain adequate immunogenicity in the post-transplant period despite immunosuppression.

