## \*Notes:

- i) Living and Deceased Donor Transplant Recipients: The study was originally restricted to participants who were expecting to receive only living donor renal transplants. However, less than a third of kidney transplants in the United States occur with kidneys from living donors. A majority of transplants are in the setting of donation of kidneys from deceased donors. To permit efficiencies in accrual, the study is amended (from version 3.5) to also open enrollment to recipients of deceased donor kidneys.
- ii) Transplant recipients of both genders: The study was originally designed to be conducted only

among women. However, in October 2018, the FDA approved an age expansion indication for the Gardasil 9 HPV vaccine for both women and men up to 45 years (from the originally approved upper age limit of 26 years), thus opening a new clinical cancer preventative option for middle-age adults of both genders [38]. The primary endpoint for the study is HPV-vaccine-type-specific seroconversion rates, which are not expected to be differential by gender, based on extrapolating from the uniformly high (>99%) seroconversion rates observed regardless of gender in studies among immunocompetent individuals. However, HPV vaccine-type-specific titer levels (GMT) differences by gender will be analyzed as a secondary endpoint, given variability in immune response titer levels observed between males and females in immunocompetent individuals (related to the differences in body mass index or hitherto unproven factors related to hormone-immune interactions [20,21]). Another advantage of expanding this study to males will be to facilitate efficiencies in accrual, since men constitute the majority (55%-65%) of all kidney transplant recipients in the United States. Although a majority of current HPV-associated cancers among solid organ transplant recipients occur among women, [2] there is increasing evidence of the link between HPV infection and oropharyngeal cancers that disproportionately affect men [39]. HPV-related oropharyngeal cancers are now the most common HPV-related cancers in the United States, surpassing even the incidence of cervical cancer. [39] The expansion of enrollment to men will also allow this study to look at the effect of HPV vaccination on persistence of oral HPV infection as a secondary/exploratory endpoint in the context of transplantrelated immunosuppression.

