#### 13. STATISTICAL CONSIDERATIONS

#### 13.1 Study Design/Description

This is a prospective single-arm trial to evaluate if the Gardasil® 9 HPV vaccine induces and sustains an adequate immune response at 12-months post-transplantation among 18-49 year old kidney transplant recipients when ≥ 1 doses of the vaccine are administered prior to transplantation. The study population includes candidates for renal transplant within 12 months of enrollment at five transplant centers in the United States. We anticipate that 96 eligible kidney transplant recipients will ultimately be enrolled and complete follow-up during the study period of 36 months, and 24-28 of them will have received the second vaccine dose before their transplant. For the analytical dataset for the primary endpoint, participants will have received the first dose of Gardasil® 9 nonavalent HPV vaccine at baseline and their post-transplant serology titers are assessed at 12-months post-transplant visit. Kidney transplant candidates who receive one or two doses of the vaccine but do not get transplanted within 12 months of enrollment will be considered off-study after they are offered the remainder of the vaccine doses to complete the three-dose vaccine series.

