# 13.5 Secondary and Exploratory Objectives, Endpoints, Analysis Plans

#### Secondary Endpoint:

Descriptive statistics, such as probabilities and exact 95% confidence intervals, will be used to summarize HPV vaccine-type-specific seroconversion rates at 6- and 12-months post-transplantation stratified by number of doses (1, 2, or 3) of the vaccine given pre-transplant. Seroconversion probabilities will be compared between dose groups using Fisher's exact test. Armitage trend test will be used to examine whether there is a trend for increased seropositivity across dose groups. Due to the limited sample size, these tests will be sufficiently powered to detect only very large differences and will be considered exploratory.

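### Section 13.4 names two unreconciled primary intervals and tabulates only upper limits, although whether the response is adequate depends on the lower limit

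*Combined protocol and SAP*

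**What the plan says.** Section 13.4 describes the primary interval twice.

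- Near the start: "An estimate of the seroconversion rate will be provided along with exact Clopper-Pearson 95% confidence intervals (CIs". The number of sides is not stated.
- Further down, on the redesign in version 3.11 for 24 to 28 evaluable participants, the focus is narrowed to the "description of the estimation of the seroconversion rate and the upper limit of its one sided 95% confidence interval", in place of pre-specified comparisons.

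The only precision statement in the section is "Table 3. Expected upper limits of one sided 95% CI for seroconversion rates". It covers assumed estimates of 0.65, 0.70, 0.75, 0.80 and 0.90 at n=24 and n=28, and it has no lower-limit column.

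Four other places bear on the point.

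- Section 13.1 says the trial evaluates whether the vaccine "induces and sustains an adequate immune response at 12-months post-transplantation among 18-49 year old kidney transplant recipients". The hypothesis at the end of section 2.3 is that vaccination before transplant "will induce and maintain adequate immunogenicity in the post-transplant period despite immunosuppression".
- Section 2.3 also still states: "we will define efficacy as greater than or equal to 90% of the study population achieving seroconversion".
- The secondary endpoint in section 13.5, which includes the same 12-month rates split by number of doses, is planned as follows: "Descriptive statistics, such as probabilities and exact 95% confidence intervals, will be used to summarize HPV vaccine-type-specific seroconversion rates".
- The notes to section 4.1.1 mention "uniformly high (>99%) seroconversion rates observed regardless of gender in studies among immunocompetent individuals".

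**The concern.** An unqualified 95% confidence interval is conventionally two-sided, so the opening statement of 13.4 implies both a lower and an upper limit. The later statement, with its word for exclusivity, implies a point estimate and one upper limit. Two analysts following the same section could report different primary intervals, one of them with no lower limit. The dose-group results in 13.5 could then carry a different kind of interval from the overall rate.

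The choice of side also does not fit the question. If the question is whether the rate is high enough, the reader needs to know how low it could plausibly be. An upper limit below some level shows that the response falls short of that level; an upper limit near 1 does not show that the response is good. If the vaccine works as hypothesised, the upper limit will be close to 1 almost whatever is observed.

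Section 13.4 gives cross-study comparison and preparation for larger studies as the purposes of the redesigned analysis. Both need the lower limit as well as the upper.

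**Working it through.** **Inputs.** n = 24 and 28; assumed estimates P = 0.65, 0.70, 0.75, 0.80, 0.90; one-sided 95% (all from section 13.4 and Table 3). The 0.90 efficacy level is from section 2.3.

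**Formulas (exact Clopper-Pearson, x responders out of n).** Beta(q; a, b) is the q-quantile of the beta distribution.

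- One-sided 95%: upper = Beta(0.95; x+1, n−x); lower = Beta(0.05; x, n−x+1).
- Two-sided 95%: from Beta(0.025; x, n−x+1) to Beta(0.975; x+1, n−x).
- If x = n, the upper limit is 1 and the lower limit reduces to 0.05^(1/n) one-sided or 0.025^(1/n) two-sided.

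**Step 1: reproduce Table 3 and add the missing side.** Setting x = nP without rounding gives all ten printed values to within 0.0001.

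| n | P | x = nP | Upper, printed | Upper, recomputed | One-sided lower, not printed |
|---|---|---|---|---|---|
| 24 | 0.65 | 15.6 | 0.8088 | 0.8087 | 0.462 |
| 24 | 0.70 | 16.8 | 0.8480 | 0.8480 | 0.513 |
| 24 | 0.75 | 18 | 0.8851 | 0.8851 | 0.565 |
| 24 | 0.80 | 19.2 | 0.9197 | 0.9197 | 0.620 |
| 24 | 0.90 | 21.6 | 0.9776 | 0.9776 | 0.739 |
| 28 | 0.65 | 18.2 | 0.7977 | 0.7977 | 0.477 |
| 28 | 0.70 | 19.6 | 0.8380 | 0.8380 | 0.528 |
| 28 | 0.75 | 21 | 0.8763 | 0.8763 | 0.581 |
| 28 | 0.80 | 22.4 | 0.9123 | 0.9123 | 0.636 |
| 28 | 0.90 | 25.2 | 0.9739 | 0.9739 | 0.755 |

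The table is therefore correct for what it claims to show. Only the two 0.75 rows (18/24 and 21/28) are results that could be observed; the other eight imply fractions of a person.

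**Step 2: do the two statements give different numbers?** Yes, on the two-sided reading of the first. For 18/24 the upper limit is 0.885 one-sided and 0.902 two-sided, so the two fall on opposite sides of 0.90.

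**Step 3: what each bound conveys when the response is good.** These are the attainable results of 90% or more.

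| Result | One-sided upper | Two-sided lower |
|---|---|---|
| 22/24 | 0.985 | 0.730 |
| 23/24 | 0.998 | 0.789 |
| 24/24 | 1.000 | 0.858 |
| 26/28 | 0.987 | 0.765 |
| 27/28 | 0.998 | 0.817 |
| 28/28 | 1.000 | 0.877 |

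The upper limit moves by 0.015 at n=24 (1.000 − 0.985) and by 0.013 at n=28 (1.000 − 0.987). The lower limit moves by 0.128 (0.858 − 0.730) and by 0.112 (0.877 − 0.765).

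**Step 4: can 24 to 28 participants confirm 90%?** The best possible result is that everyone seroconverts.

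- One-sided lower: 0.05^(1/24) = 0.8827; 0.05^(1/28) = 0.8985; 0.05^(1/29) = 0.9019.
- Two-sided lower: 0.025^(1/24) = 0.8575; 0.025^(1/28) = 0.8766; 0.025^(1/35) = 0.89997; 0.025^(1/36) = 0.9026.

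No result in the planned range puts a 95% lower limit at or above 0.90. An all-positive sample first does so at n=29 one-sided or n=36 two-sided.

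**The case against.** The strongest reply is that the lower limit is already planned: the opening sentence of 13.4 is the reporting commitment, a two-sided reading supplies both limits, and the later restriction only signals that benchmark tests were dropped. That is a possible reading, but the number of sides is never stated, and the later sentence and Table 3 both point to a one-sided upper limit. If two-sided intervals are intended, that sentence and the table contradict the intention; if they are not, the lower limit is lost. The text needs an edit either way.

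A second reply is that the upper limit is not empty. This stands in part. At observed rates of 0.65 to 0.75, every Table 3 upper limit (0.7977 to 0.8851) is below 0.90, so a poor response would be shown to fall short of the section 2.3 level. The upper limit loses its value where the hypothesis is true.

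A third reply is that the redesigned analysis is descriptive, with no decision rule attached to either bound, and that a reader given the counts can compute any limit. It is true that no decision is put at risk, and this limits the seriousness. But a descriptive aim is a reason to show both limits, and 13.4 gives no reason for preferring the upper one.

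Some supporting points are minor. Table 3 is illustrative, so its fractional counts do no harm by themselves. The figure above 99% concerns immunocompetent people and is not a planning assumption here; it shows only that results above 0.90, where Table 3 stops, should be covered. Small numbers remain a limit whichever side is reported.

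**Conclusion.** The concern holds and should be fixed. Section 13.4 leaves the primary interval ambiguous, and the bound it singles out cannot support the claim of an adequate response. At Table 3's own estimate of 0.90, a reader sees 0.978 or 0.974 and does not see that the one-sided lower limit is 0.739 or 0.755.

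The statement that there are two different intervals rests on the conventional two-sided reading of an unqualified 95% interval; without that reading the section is still ambiguous. All limits assume exact Clopper-Pearson intervals and 24 or 28 evaluable participants. The lower limits set beside Table 3 use its fractional counts; the other limits use whole counts.

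**What to change.** In section 13.4, delete the one-sided upper-limit focus and state:

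> For each vaccine type, the 12-month seroconversion rate will be reported with its two-sided exact Clopper-Pearson 95% CI; this is the only interval for the primary endpoint.

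Replace Table 3 with both limits at attainable counts up to 100%:

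| n=24 | Two-sided 95% CI | n=28 | Two-sided 95% CI |
|---|---|---|---|
| 16/24 | 0.447–0.844 | 18/28 | 0.441–0.814 |
| 18/24 | 0.533–0.902 | 21/28 | 0.551–0.893 |
| 20/24 | 0.626–0.953 | 23/28 | 0.631–0.939 |
| 22/24 | 0.730–0.990 | 26/28 | 0.765–0.991 |
| 23/24 | 0.789–0.999 | 27/28 | 0.817–0.999 |
| 24/24 | 0.858–1.000 | 28/28 | 0.877–1.000 |

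In section 2.3, describe the 90% level as a descriptive reference for the observed proportion, first met at 22/24 (91.7%) or 26/28 (92.9%). Add that 24 to 28 participants cannot confirm it with a 95% lower limit.

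The cost is two wording edits and one recalculated table, with no new data or visits. The stated precision will look less favourable, and two-sided upper limits are slightly higher than those now printed (18/24: 0.902 against 0.885).

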# 13.5 Secondary and Exploratory Objectives, Endpoints, Analysis Plans

#### Secondary Endpoint:

Descriptive statistics, such as probabilities and exact 95% confidence intervals, will be used to summarize HPV vaccine-type-specific seroconversion rates at 6- and 12-months post-transplantation stratified by number of doses (1, 2, or 3) of the vaccine given pre-transplant. Seroconversion probabilities will be compared between dose groups using Fisher's exact test. Armitage trend test will be used to examine whether there is a trend for increased seropositivity across dose groups. Due to the limited sample size, these tests will be sufficiently powered to detect only very large differences and will be considered exploratory.

### Exploratory Endpoints:

- 1) Descriptive statistics, such as probabilities and exact 95% confidence intervals, will be used to summarize probability of seroconversion at 12 months post-transplant for the following groups:
  - a) time elapsed between last vaccine dose and the transplant procedure, e.g. <3 months vs. >3 months. Different groupings will be considered based on observed (e.g. median) and clinical considerations. Time will be summarized using descriptive statistics, e.g. median, interquartile range, or range; groups defined by dosing and types of post-transplant immunosuppressant medications, as well as;
  - b) type of transplant surgery (living donor/deceased donor);
  - c) differences in Human Leukocyte Antigen (HLA) histocompatibility between donor and recipient:
  - d) differences by biological sex (i.e., male vs. female) of the transplant recipient.
- 2) Stability of HPV vaccine-type-specific geometric mean titers (GMT) at 6 and 12- months post-transplantation, and rise in HPV vaccine-type-specific GMT at the 13 month post-transplant visit.
  - a) Stability will be evaluated in relation to changes in the type-specific GMTs between the two post-transplant time points (6- and 12-months post-transplant) and reported as follows: (i) decrease: more than 2-fold decrease, (ii) stable: within 2-fold change, and (iii) increase: greater than 2-fold increase.
  - b) The magnitude of increase in type-specific GMTs at the 13-month post-transplant visit (i.e., 1 month after the booster dose) will be described in relation to the type-specific GMTs at the other post-transplant visits (6 and 12-months post -transplant). Patterns over time will also be explored using graphical techniques.
  - c) Stability, and post-booster dose increase in type-specific GMTs will also be described in relation to the number of vaccine doses (1, 2 or 3) received in the pre-transplant period.
- 3) Vaccine safety profile and allograft rejection/opportunistic infections will be summarized using descriptive statistics, stratified by number of vaccine doses and time between the last vaccine dose and the transplant procedure.
- 4) HPV detection in samples from the anogenital, and oral cavity specimens at baseline (prevaccination) and at 6- and 12-months post-vaccination, overall and by number of vaccine

doses (1, 2, or 3), sexual behavior, type-specific seroconversion rates, and time elapsed between the last vaccine dose and the transplant procedure. All rates of HPV detection will be specified, overall and stratified by number of doses (1, 2, or 3) and time to transplant.

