## **Exploratory Endpoints**

- 1) HPV vaccine-type-specific seroconversion rates at 12-months post-transplantation stratified by:
  - a) time elapsed between last vaccine dose and the transplant procedure;
  - b) variations in doses and types of post-transplant immunosuppressant medications; and interactions with type of transplant surgery (living donor/deceased donor);
  - c) differences in Human Leukocyte Antigen (HLA) histocompatibility between donor and recipient;
  - d) differences in biological sex (i.e. male vs. female) of the transplant recipient.
- 2) Stability of HPV vaccine-type-specific geometric mean titers (GMT) at 6- and 12-months post-transplantation and rise in HPV vaccine-type-specific GMT at the 13-month post-transplant visit.
- 3) Vaccine safety profile and allograft rejection/opportunistic infections stratified by number of vaccine doses and time between the last vaccine dose and the transplant procedure.
- 4) HPV detection in samples from the cervix/vagina, and oral cavity at baseline (pre-vaccination) and at 6- and 12-months post-vaccination, overall and by number of vaccine doses (1, 2, or 3), sexual behavior, type-specific seroconversion rates, and time elapsed between the last vaccine dose and the transplant procedure.

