# 13.6 Reporting and Exclusions

We anticipate some drop-outs due to transplantation complications, health deterioration, or death. The drop-out rate is expected to be 20%, resulting in a final sample of 24-28 participants who complete the study.

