#### **Procedures:**

- 1. Study staff will identify appropriate participants affected by the cancellation/deferral of regularly scheduled study visits.
- 2. Eligible participants will be contacted by phone and procedures will be explained by the study investigators and staff.
- 3. Participants will be administered the remote consent as per COVID-19 remote consent procedures approved by the CIRB. (see 'Appendix H')
- 4. Staff will interview the participants for review of medical and surgical history, medications, symptom assessment, determination of ECOG performance status, and follow-up questionnaire for the 6-months and 12-months visits.
- 5. Participants will be sent an Evalyn cervical/vaginal specimen collection kit, and a Neoteryx Mitra sampling cartridge. All collection kits will have standardized instructions and study specific information sheets (see 'Finger Stick Participant Information material' and 'Vaginal Self-Collection Instructions'). All devices and return collection kits will have barcoded labels that confidentially link back to the participant record without any identifying information (participant name, other contact details, etc.).
- 6. Participants will self-collect a personal cervical/vaginal specimen and a finger stick blood specimen and will return to the Cedars Sinai biorepository using pre-labeled, pre-paid packages that will be picked up by a courier at the participant's home or pre-arranged location.

- 2. **Expansion of window for 12-months post-transplant visit for specimen collection for primary endpoint:** The visit for specimen collection for the primary endpoint (12-months post-transplantation time point) is regularly scheduled at 12-months +/- 2 weeks after the transplant surgery. The +/- 2 weeks window will now be extended to *up to +/- 6 months* to permit maximum operational flexibility due to the scheduling challenges due to COVID-19, and may be rescheduled to a convenient date and time once it is considered safe to resume study activities.
- 3. **6-months post-transplant study visits:** The rescheduled 12-month post-transplant visit (for the primary endpoint) now includes a very broad/expanded window (+/- 6 months) that may overlap with the original 6-month post-transplant visit timeframe. The 6-month post-transplant visit will therefore be considered an optional one due to the COVID-19-related scheduling challenges.

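### The 2-fold stability categories are applied to group GMTs, so one label per HPV type can hide substantial titre loss in individual participants

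*Combined protocol and SAP*

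**What the plan says.** Sections 1.3 and 8.2 name the endpoint at group level: "Stability of HPV vaccine-type-specific geometric mean titers (GMT) at 6- and 12-months post-transplantation". Section 13.5, item 2(a), gives the method: "Stability will be evaluated in relation to changes in the type-specific GMTs between the two post-transplant time points", with the categories "i) decrease: more than 2-fold decrease, (ii) stable: within 2-fold change, and (iii) increase: greater than 2-fold increase". Item 2(c) carries the same quantity into dose groups: "Stability, and post-booster dose increase in type-specific GMTs will also be described in relation to the number of vaccine doses". The only other longitudinal description is in item 2(b): "Patterns over time will also be explored using graphical techniques". It does not say whether the graphs show individual participants.

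The documents define no participant-level fold change, no count of participants per category and no confidence interval for the GMT ratio. They do not restrict the two GMTs to participants sampled at both visits.

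On numbers, Section 13.6 states: "The drop-out rate is expected to be 20%, resulting in a final sample of 24-28 participants who complete the study". The main protocol schedules the 6-month visit for every transplanted participant (Sections 7.1 and 7.4). Under the COVID-19 contingency plan (Appendix G, item 3) this changes: "The 6-month post-transplant visit will therefore be considered an optional one due to the COVID-19-related scheduling challenges". Item 2 of the same appendix widens the 12-month window from 2 weeks to as much as 6 months either side.

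**The concern.** The trial asks whether antibody is maintained after transplant under immunosuppression, and Section 2.3 lists variation between people in peak and plateau titres among the open research questions. A ratio of two group GMTs averages that variation away. A type can be labelled stable while a sizeable minority, or even half, of the participants lose several-fold.

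The seroconversion endpoints do not fill the gap. They show a loss only when it takes someone below the Section 9.1.1 cut-off. A participant at 8 times the cut-off who loses 4-fold is still at twice the cut-off and counts as seropositive at both visits.

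A second, smaller issue is composition. If the people contributing to the two GMTs differ, the ratio can move although nobody's titre has changed.

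What is at stake is the value of the description. Under version 3.11 (Section 13.4) the study is descriptive and is meant to supply preliminary data for larger trials.

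**Working it through.** The plan gives no precision or sample-size figure for this endpoint and no titre SD, so there is no stated figure to reproduce.

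**Inputs.** Evaluable n = 24 to 28 (Sections 13.3, 13.4 and 13.6). Cut-offs on the 12-month/6-month GMT ratio (item 2(a)): below 0.5 is a decrease, 0.5 to 2 is stable, above 2 is an increase. Every SD below is an assumption.

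**1. Losses compatible with a stable label (no SD needed).** In complete pairs the GMT ratio is the geometric mean of the individual fold changes. If k of n participants lose f-fold and the rest are unchanged, ratio = f^(−k/n).

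| n | fold loss f | largest k still stable | share | ratio |
|---|---|---|---|---|
| 24 | 4 | 12 | 50% | 4^(−12/24) = 0.50 |
| 24 | 8 | 8 | 33% | 8^(−8/24) = 0.50 |
| 24 | 16 | 6 | 25% | 16^(−6/24) = 0.50 |
| 28 | 4 | 14 | 50% | 4^(−14/28) = 0.50 |
| 28 | 8 | 9 | 32% | 8^(−9/28) = 0.51 |
| 28 | 16 | 7 | 25% | 16^(−7/28) = 0.50 |

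A ratio of exactly 0.50 is the boundary; the plan calls a type decreased only beyond 2-fold. One participant fewer is clearly inside: with n = 24, 11 people losing 4-fold gives 4^(−11/24) = 0.53.

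**2. Share with more than a 2-fold loss at a given group ratio r.** Assume log2 fold change ~ Normal(log2 r, SD). Share = Φ((−1 − log2 r)/SD).

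| r | SD 0.5 | SD 1 | SD 1.5 | SD 2 |
|---|---|---|---|---|
| 1.0 | 2% | 16% | 25% | 31% |
| 0.6 | 30% | 40% | 43% | 45% |

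For example, r = 1.0 and SD = 1 give Φ(−1) = 0.159.

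**3. Different people at the two visits, with nobody's titre changing.**

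- *Missingness related to titre.* Of 24 people, 8 have 10-fold lower titres and no 6-month sample. Ratio = 10^(−8/24) = 0.46, labelled a decrease. If instead titres are log-normal and the lowest third lack a 6-month sample (16 of 24 present), the simulated ratio is about 0.62, 0.48 and 0.38 for a log10 SD of 0.4, 0.6 and 0.8.
- *Random missingness.* With m of n sampled at 6 months, the log10 ratio has SD s × √(1/m − 1/n), and a false label needs it to exceed log10 2 = 0.301 in size. For s = 0.4, 0.6 and 0.8, the chance is below 1% throughout with 16 of 24 present, and about 0.02%, 1.4% and 6.5% with 12 of 24.
- *Small dose group, random missingness.* Suppose three equal dose groups (24/3 = 8) with 4 of 8 sampled at 6 months. For s = 0.6 the SD is 0.6 × √(1/4 − 1/8) = 0.212, z = 0.301/0.212 = 1.42 and the chance is 16%. For s = 0.4 and 0.8 it is 3% and 29%.

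**4. Interval.** With the contingency window, the 12-month sample may fall between 6 and 18 months. Against a nominal 6-month sample the interval runs from 6 − 6 = 0 to 18 − 6 = 12 months, while the 2-fold cut-off stays fixed.

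**The case against.** The endpoint is declared as stability of GMT, and item 2(a) analyses that. A GMT fold change is a coherent summary: in complete pairs it gives the average change correctly and loses only the spread. Losses that cross the cut-off appear in the primary and secondary seroconversion rates, and graphs over time are planned. The note on both genders under Section 4.1.1 uses GMT loosely for titre levels, so the authors may have meant individual titres here. Some individual 2-fold shifts will be assay noise, and the documents give no assay precision to judge how many.

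All of this is fair, and it keeps the point small. It does not remove it. The text as written categorises a group quantity, losses above the cut-off go unreported, and the graphs are not stated to be per participant. If individual titres were intended, the change only states the intention.

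Stronger readings are tempting, and the documents do not support them:

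- *The plan prescribes an unpaired comparison.* It does not; it is silent on pairing.
- *The 6-month visit is optional.* It is optional only under the COVID-19 contingency plan, which also offers home blood collection for that visit and so helps preserve samples.
- *A third to a half of participants could have hidden losses at a group ratio of 1.0.* At SDs of 1 and 1.5, 32% and 50% change more than 2-fold in either direction; losses alone are half that, 16% and 25%.
- *Missing visits will distort the label.* For the full group with random missingness this is unlikely (step 3), and nothing in the documents ties missed visits to titre.

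**Conclusion.** The point stands as a minor improvement to an exploratory analysis. Item 2(a) yields one label per HPV type, or per type and dose group, and that label can read stable with up to half of the participants losing 4-fold or a third losing 8-fold. This follows from the rule alone. The 16% and 25% at a group ratio of 1.0 rest on a Normal model and on assumed log2 SDs of 1 and 1.5; over SDs of 0.5 to 2 the range is 2% to 31%.

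The composition issue is a possibility left open by the absence of a both-samples rule. It becomes material if missingness relates to titre or where dose groups are small.

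A reader might infer that the trial's conclusion on maintained immunity is at risk. It is not: the primary endpoint is the 12-month seroconversion rate, and no test or decision uses the stability label.

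**What to change.** Reword item 2(a) so that, for each HPV type and among participants with both samples:

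- each participant's 12-month/6-month titre ratio is computed, and the number and percentage in each of the three 2-fold categories are reported;
- the paired geometric mean ratio is given with its 95% CI;
- the number with only one of the two samples is stated, along with the actual interval between samples where the contingency window was used, and how titres below the assay limit enter the ratio.

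Use the same layout by number of doses under item 2(c), with counts shown because the groups will be small. The group GMTs at each visit can still be presented.

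The cost is SAP wording and slightly more analysis work on the same data. The paired set will be somewhat smaller than the 12-month set, and some individual 2-fold shifts will reflect assay noise, which the report should say. The wording is best settled before the batch serology planned for the end of the study (Section 10.2.1).
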